This study will focus on obtaining a special type of scalp EEG recordings (high-density EEG) and electrical impedance measurements in patients with neurological disorders (i.e., epilepsy, brain tumor, stroke, etc.) and appropriately matched controls. High-density EEG (hdEEG) is a scalp EEG which uses up to 256 channels compared to the standard 21 channels used for routine clinical applications. The reason for using more channels to record is for more precise localization of epileptogenic foci and/or more precise mapping of brain functions. To that end, it is optimal to utilize subject's own MRI scan to create the modeling for hdEEG analysis. Electrical impedance can be measured using the same electrodes as EEG or other electrodes interspersed between the EEG electrodes or placed at other anatomic locations. Electrical impedance provides a measure of electrical tissue properties as opposed to brain function by injecting safe and imperceptible current (I) at a given frequency into selected pairs of electrodes and recording the corresponding voltage differences (V) across other electrode pairs, i.e. $Z = V/I$. By using high-density electrodes, much like hdEEG, electrical impedance measurements can be combined to produce an image of the electrical properties of the brain tissue (a process called Electrical Impedance Tomography (EIT)). Alternatively, a smaller subset of electrodes can be used to acquire measurements over a frequency range (a process called Electrical Impedance Spectroscopy (EIS)) that can yield gross information across regions of the tissue. All of these techniques (EIT, EIS and hdEEG) may provide clinically useful information for a number of neurological disorders where there is significant change to brain tissue.

2. Objectives and Hypotheses

This study is aimed at 1) using scalp high-density EEG (hdEEG) for localizing epileptic activity and/or studying brain functions in patients with certain neurological disorders, and 2) using the same (or similar interspersed) electrodes to acquire electrical impedance images (EIT) or record spectral impedance signatures (EIS) of neurological disorders. The experiments that we perform will involve measurement of brain activity and tissue in patients with neurological disorders (i.e., epilepsy, brain tumor, stroke, etc.) and controls using a novel scalp hdEEG system and custom EIT/EIS systems.

hdEEG: We plan to localize the sources of interictal epileptiform activity during resting state for patients with seizures, and map brain activity during presentation of tasks. The development, testing and refinement

of the various tasks will be an ongoing process of multidisciplinary collaboration among a variety of co-investigators representing the Department of Psychiatry ([name]), Department of Neurology ([name], [name], [name], [name], [name], [name]), and Section of Neurosurgery ([name], [name], and [name]). Testing will investigate the localization of a wide variety of brain functions, including: sensation, movement, hearing, vision, speech, memory, social cognition, and emotion. As such, a variety of hypotheses regarding the localization of specialized brain functions and their disruption by certain neurological disorder processes will be evaluated in the course of this work. The purpose of this study is to use the hdEEG for improved localization of critical brain functions important for further understanding of the brain in health and disease, and also planning surgical intervention if warranted.

EIT/EIS: EIT and EIS represent promising technologies to image or characterize the brains of stroke patients because there are significant conductivity differences between normal, ischemic, and hemorrhagic (blood) tissue. This electrical information may help to 1) identify the onset of a stroke, 2) discriminate hemorrhagic from ischemic stroke, 3) provide reliable automatic and continuous monitoring of stroke patients after stabilization aims will be an ongoing process of multidisciplinary collaboration among co-investigators representing the Department of Neurology ([name], [name], [name], [name], [name], [name]) and the Thayer School of Engineering ([name], [name], [name]).

3. Study Design

Describe all study procedures, materials, and methods of data collection:

hdEEG System: High-density EEG recordings will be obtained via the EGI Geodesic EEG 400 designed for research applications. This system is available through the Department of Neurology and Department of Psychiatry at DHMC. This EEG system uses a 256 (or 128) channel cap to record EEG signals during the resting state and during the performance of functional or cognitive tasks.

EIT/EIS Systems: The EIT and EIS data collection will use custom systems owned by the Thayer School of Engineering at Dartmouth and housed in the Williamson Building at DHMC. The EIT/EIS data collection will be conducted only on stroke patients and healthy control subjects in this study. Electrical impedance systems are well established as patient safe and are commonly used in bioelectrical body impedance analysis [a], lung monitoring [b], breast cancer research [c], stroke research [d] and other research. **EIT system.** The EIT system (Fig. 1A) is a broadband (100 Hz–10 MHz) 20-channel data acquisition (DAQ) system with a SNR > 90 dB which possesses high speed capabilities (up to 80 frames/ second) [e]. The system is flexible and has a modular hardware and software design that allows for performance upgrades such as DAQ frame rate and SNR. It uses National Instruments (NI) hardware and software modules, which offer inherent compatibility over generations of hardware and software revisions. Digital switches allow data to be recorded from up to 120 electrodes. **EIS system.** The EIS system operates similarly to the EIT system. However, it will only use up to 30 channels. The custom-designed system allows for switching between channels and applies currents over a bandwidth of 100 Hz-500 kHz. Prior versions of both the EIT and EIS systems have been safely implemented in other IRB-approved human subjects studies here at DHMC [f]. The EIT and EIS systems comply with International Electrotechnical Commission (IEC) requirements for safety and essential performance of medical electrical equipment (IEC 60601-1). The EIT system has been reviewed and approved by DHMC Biomedical Engineering. The EIS system is the next iteration of this and will be approved by DHMC Biomedical Engineering prior to any patient use.

Optical Scanners:

The optical scanners are used to recover precise locations of electrodes and landmarks, e.g. nasion (bridge of nose), left and right pre-auricular points, for registration with the MR imaging data. The scanners will either be a Geodesics Photogrammetry System 3 (GPS3)

(<https://www.philips.com.tw/healthcare/product/HC4601902/geodesic-photogrammetry-system-3-research->

[gps](#)) or a research-only iPhone/iPad (password protected) using a 3D scanning application. The GPS3 software allows via a semi-automated process to output electrode and landmark positions. Thus subjects' photographs will be immediately deleted after positions are output. The iPhone/iPad application (i.e., Heges, Capture) performs all 3D scanning calculations locally and scans will immediately be transferred to approved research computers and original scans on the iPhone will be deleted. Secondary, checks will be performed on the scans and if any identifiable information remains in the scans they will be removed.

Studies

There will be three types of studies: short-term hdEEG study, short-term hdEEG/EIT/EIS study, and long-term hdEEG study. For short-term study, the study duration is up to 2 hours. For long-term study, it will be at least an overnight recording.

1) Short-term hdEEG study (Epilepsy, Brain tumor, Peripheral nerve)

A patient with neurological disorder (i.e., epilepsy, brain tumor, peripheral nerve dysfunction, etc.) or control subject will be studied as an outpatient in the EEG lab. The subject will have the 256 or 128-channel cap placed and a special type of photograph of the EEG cap and subject's head will be taken using a Photogrammetry system which allows for better source modeling of electrophysiological signals. The subject will subsequently recline on a chair or bed and either rest (i.e., attempt to fall asleep) and/or perform specific tasks. We expect that experiments will usually be completed in 1 session lasting 60-120 minutes. For patients with peripheral nerve dysfunction, we expect to conduct 2 sessions of recording, one before their surgical procedure, and one during their post-operative follow-up visit to assess the peripheral nerve function recovery.

2) Short-term hdEEG/EIS/EIT Study (Stroke, Control)

Patients recently stabilized after an acute stroke or healthy volunteers serving as control subjects will be recruited and consented to participate in this study. Control subjects and patients that can safely be transported will have data collected in the EEG lab, where all of the EEG equipment is normally located. Patients that cannot be transported will have their data collected in their inpatient room. A cap will be placed on their head with up to 256-channels for EEG and EIT and up to an additional 30 EIS electrodes (described below). A special type of photograph of the EEG cap, other electrodes and patient's head will be taken using either the Photogrammetry system in 3C or a portable optical scanning unit described previously. The 3D scan of the head, cap, and electrodes produced via photogrammetry allows for better modeling of electrical tissue parameters and sources of electrophysiological signals. Patients will subsequently recline on a chair or bed and either rest (i.e. try to fall asleep) or perform specific tasks. We expect the experiment will be completed in a session lasting approximately 90-120 minutes. We will record 1) 10 minutes of resting state hdEEG, 2a) ~10 minutes of EIT data from the EEG cap electrodes and/or 2b) ~30 minutes of EIS data from a subset of electrodes, and 3) an additional ~20 minutes of hdEEG while the study participant performs a sensorimotor assessment. NIH stroke scale/score (NIHSS) and general clinical information (i.e., type of stroke, laterality, etc.) will be assessed by consenting physicians. A second data collection may be performed at 2-3 months post-stroke during a routine outpatient follow-up appointment, based on the patient's condition and willingness to participate. At this visit, the same protocol will be performed, and NIHSS may be assessed.

A brain MRI scan may not be part of their standard care, we will obtain permission to access their head CT scans, if available. Otherwise, we will use a standard brain atlas (<https://www.mcgill.ca/bic/software/tools-data-analysis/anatomical-mri/atlas/mni-305>) for their hdEEG analysis.

On a subset of ~15 patients (based on budget constraints) a brain MRI scan may also be performed during follow-up appointments. If an individual is not able to participate in the MRI scan for any reason, they will not be excluded from the study. Subject can choose not to participate in the follow-up MRI scan. MRI scan that is done solely for study purposes will not be billed to subject's insurance. Incidental findings, if any, will be shared with the subject (and their LAR, if applicable) and documented in their medical records.

Pregnant persons will be excluded in this study. Persons of childbearing age will be questioned regarding pregnancy in addition to undergoing a urine pregnancy test before MRI scan. If the urine pregnancy test is

positive, the subject will be excluded. Subjects will be told the results. Because full confidentiality regarding pregnancy cannot be entirely guaranteed, these testing requirements and the limited scope of confidentiality will be made known to the subject during the consent procedure. In this manner, anyone who would not be comfortable with pregnancy testing or sharing the results of such testing can “opt out” of the study at the time of the initial consent, without having to declare any specific reasons.

For control subjects, we will not obtain their individual MRI scans. Instead, we will use the standard brain atlas (<https://www.mcgill.ca/bic/software/tools-data-analysis/anatomical-mri/atlas/mni-305>) for the hdEEG analysis.

3) Long-term hdEEG study (Epilepsy)

Patients with epilepsy admitted to the Epilepsy Monitoring Unit (EMU) will be consented to participate in this study on one of the days of his/her admission. A 128-channel (or 256-channel) long-term monitoring (LTM) net (gel-based) will be placed on the patient’s head in the EMU. hdEEG will be recorded overnight in addition to the clinical video-EEG. There will be no control subject enrolled in this study. We expect the experiment will be completed in 6-24 hours, depending on the subject’s specific situation. A special type of photograph of the EEG cap, other electrodes and patient’s head will be taken using either the Photogrammetry system in 3C or a portable optical scanning unit described previously.

hdEEG Data Management

The primary form of data analysis will be the extraction and localization of event- or task-related EEG signals using synchronous averaging and other more sophisticated forms of signal extraction.

For some experiments, normal controls will be enrolled and their test and task scores will be used for comparison purposes. EEG data will be collected from these participants.

We will be presenting participants with a variety of tasks designed to activate regions important for language, motor, sensory, auditory, visuospatial, emotion, social cognition or memory function. The tasks used will depend on the specific situation of the patient, region of seizure onset or lesion, or type of surgical procedure planned. For instance, if patient has left frontal lobe epilepsy, language tasks may be given for characterization and localization of language areas.

In order to map the motor and sensory areas, we will ask the patient to tap their fingers on the thigh periodically during the movement task. By doing so, the mu-rhythm (8-12 Hz) will predominantly appear around the primary motor and sensory cortices. However, such activity can be easily affected by artifact and is not specific to any type of movement (i.e., arms or legs). Peripheral nerve somatosensory evoked potential (SSEP) tests will also be conducted in order to reliably activate the somatosensory area during the sensory task. A clinical evoked potential recording system (i.e., Medtronic NIM E4) will be used to send a constant current stimulus through surface electrodes to subjects’ peripheral nerves (i.e., ulnar, median, tibial, etc.). The stimulation parameters used to trigger the somatosensory evoked potential will follow the ACNS guideline (<https://www.acns.org/pdf/guidelines/Guideline-9A.pdf>). The SSEP raw data will be recorded using the hdEEG system. Other potential tasks to be used in this study will be to ask patients to speak, read, name pictures, remember words, remember actions and shapes, and to view shapes or objects. At certain instances, patients may be asked to view emotionally charged pictures or videos. Using these images is important to study and localize social and emotional brain function. For instance, the type of pictures presented may include selected pictures taken from IAPS (International Affective Picture System, <https://pdfs.semanticscholar.org/09bb/229a610acdd3150b8e0176194e7b7cf471b7.pdf>). In all tasks, only pictures and/or videos specifically vetted by the IRB will be presented.

De-identified EEG data and images collected for this study will be shared with other institutions and added to public databases of EEG data. All data released will be de-identified.

The data being released is EEG data (basically digitally encoded brain waves). The data variables include:
Spike – single epileptic spike (for epilepsy patients)
Event Marker – start and end of each event

EIT/EIS Electrodes

The EIT data collection will be accomplished only by means of the hdEEG scalp cap electrodes. The EIS data collection may use a small subset of hdEEG electrodes and additionally 1) electrodes placed at the base of the skull (standard ECG, stick-on electrodes), 2) custom orbit electrodes (applied to the skin surface) (see Fig. 1C), and 3) soft-palate electrodes (see Fig. 1B). The orbit electrodes will make contact with the skin on opposite sides of the nose without contacting the eye. The soft-palate electrodes are standard surface EMG electrodes which are secured to a sterile lattice which sits safely on the roof of the mouth (much as a mouth guard would). Alternatively, standard flexible Ag/AgCl hydrogel (Cadwell) electrodes which do not require the rigid lattice to secure to the roof of the mouth may be chosen to improve patient comfort. Data from the soft-palate electrodes will only be collected in 3 minute windows at the beginning and end of the session, at which time the patient will be closely monitored to eliminate the possibility of choking. Furthermore, both the orbit and all soft-palate electrodes are single-use and will be replaced between patients, and all scalp electrodes will be sterilized between uses.

[figure not shown]

Figure 1. A. Custom 20-channel EIT system, B. Soft-palate electrodes, and C. Orbit electrodes. The soft-palate electrodes are integrated into a mouth-guard like device that the patient bites down on which reduces the possibility of choking on the device and secures the electrodes to the roof of the mouth. Self-adhesive standard EEG electrodes may be used as alternatives for the soft palate if the patient shows discomfort to the rigid lattice. All electrodes will be safely secured outside of the mouth and closely monitored to reduce the possibility of choking.

- [a] Kahraman A, Hilsenbeck J, Nyga M, et al. Bioelectrical impedance analysis in clinical practice: implications for hepatitis C therapy BIA and hepatitis C. *Virol J.* 2010;7:191. Published 2010 Aug 16. doi:10.1186/1743-422X-7-191
- [b] Putensen C, Hentze B, Muenster S, Muders T. Electrical Impedance Tomography for Cardio-Pulmonary Monitoring. *J Clin Med.* 2019;8(8):1176. Published 2019 Aug 7. doi:10.3390/jcm8081176

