EEG data will be exported and pre-processed by Matlab programs developed in-house. The global field potential (GFP) and entropy across all 256 or 128 channels will be computed at each time point. GFP is sensitive to polarity changes across channels, while entropy could be helpful to eliminate EMG artifacts. Interictal epileptiform discharges (IEDs) will be identified by auto-thresholding both GFP and entropy. The source localization of IEDs will be determined using inverse solutions in Brainstorm. If applicable, intracranial EEG and/or intraoperative ECoG recordings will be used to evaluate the accuracy of IED source localizations. In addition to the self-developed detection algorithm, we will also utilize Spike Beacon software, which is developed by EGI to detect interictal discharges and compare it with our own algorithms.

For each subject, the EEG signals will be analyzed in 84 regions of interest (ROIs) defined according to the 42 Brodmann areas (BAs) for the left and right hemispheres. These ROIs will be defined for each subject using FreeSurfer. Low resolution electromagnetic tomographic analysis (LORETA) will be used to inversely estimate the EEG signal from these ROIs to localize cortical and subcortical sources from EEG signal generators. The EEG data will be investigated in the following aspects: 1) frequency content, including relative composition of delta (0.5-3 Hz), theta (3-7 Hz), alpha (7-13 Hz), beta (13-30 Hz), and gamma (>30 Hz) EEG oscillations along with their percent ratios; and 2) spatial heterogeneity, including global functional connectivity and interhemispheric asymmetry in the above-mentioned frequency bands.

For patients with peripheral nerve dysfunction, we will compare the amplitude and latency of the SSEP responses, and the source localization on individual brains between pre- and post-operative visits.

Stroke hdEEG-, EIT-, and EIS-based analysis

The aim of the hdEEG, EIT, and EIS analyses is to investigate how well these technologies function alone or in combination with each other or with other information, such as the NIHSS, CT or MRI-images to aid in 1) discriminating hemorrhagic from ischemic stroke, 2) monitoring of stroke patients, and 3) predicting stroke outcomes.

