hdEEG. The stroke hdEEG-processing will follow the steps as outlined above. In particular to stroke, we will additionally 1) perform spectral analysis to identify regions with EEG slowing (i.e., stroke region(s)), 2) use SSEP to assess sensorimotor function, and 3) investigate a novel algorithm, called EEG-No Source Imaging (NSI), which aims to localize the stroke through a hypothesis testing approach.

EIT. The collected EIT data will be used to construct 3D images of electrical properties within the head using single- and multi-frequency image reconstruction approaches. The reconstructions rely on a 3D tetrahedral mesh of the domain; nominal and patient-specific meshes will be considered. We will utilize the FreeSurfer-segmented data for this effort. We will consider reconstructions with and without structural information, e.g. skull, CSF, and stroke boundaries. Algorithms will also be considered that incorporate both EEG and EIT information. Electrical properties of the stroke, penumbra, and other ROIs will be considered for analysis.

EIS. The EIS data will look at raw impedance magnitudes and spectral properties of the acquired multi-frequency traces. Phase, magnitude, resistance, reactance and spectral fitting metrics will all be extracted

from the signals and explored in the development of a novel algorithm to isolate an intracranial abnormality, e.g., stroke region(s). This processing will include analysis of the heterogeneity of the surface potentials and will be compared to prior patient imaging to test the ability to detect, identify and localize stroke. Data will be explored in three cohorts: 1) all stroke vs all healthy 2) all ischemic vs all hemorrhagic and 3) large vs small infarct. Potential augmentation of EIS signals with EIT or EEG traces will be explored as well.

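### Stroke/control session: rest is defined as trying to fall asleep and vigilance is not scored, so drowsiness or sleep may mimic or mask the EEG slowing used as one stroke marker

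*Combined protocol and SAP*

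**What the plan says.** **The recording (section 3, Short-term hdEEG/EIS/EIT Study).** The section covers both groups: "Patients recently stabilized after an acute stroke or healthy volunteers serving as control subjects will be recruited". Its instruction is that patients recline and "either rest (i.e. try to fall asleep) or perform specific tasks". The sentence names only patients, but no separate instruction is given for controls. The itemised list begins "We will record 1) 10 minutes of resting state hdEEG" and ends with "an additional ~20 minutes of hdEEG while the study participant performs a sensorimotor assessment". No eyes-open, eyes-closed or wakefulness condition is attached to the resting block. Controls and patients who can be moved are recorded in the EEG laboratory, and the other patients in their rooms. The same protocol may be repeated 2-3 months after the stroke.

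**The analysis (section 4).** The first stroke-specific hdEEG step is to "perform spectral analysis to identify regions with EEG slowing (i.e., stroke region(s". The second and third are to "use SSEP to assess sensorimotor function, and 3) investigate a novel algorithm, called EEG-No Source Imaging (NSI". The general hdEEG processing, which the stroke analysis follows, measures "relative composition of delta (0.5-3 Hz), theta (3-7 Hz" and the higher bands, with percent ratios, global functional connectivity and interhemispheric asymmetry by band.

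**Screening (section 4, hdEEG Processing).** Artifact detection marks segments with eye movement, head movement or muscle activity. No section asks for wakefulness, scores sleep, removes drowsy segments or adjusts for state.

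**The concern.** One section invites a state that raises slow activity, and another reads slow activity as a sign of the lesion. Nothing between them separates the two sources. Attempted sleep is a natural instruction where the aim is to capture interictal discharges, and almost the same wording appears in the epilepsy, tumour and peripheral nerve session. It does not suit a session in which slowing is itself a measurement.

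Section 4 gives three aims for the stroke work: telling haemorrhagic from ischaemic stroke, monitoring patients, and predicting outcome. Each could be affected.

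- **Monitoring.** A fall in delta share between the acute visit and 2-3 months could reflect a more alert participant rather than recovery.
- **Discrimination and prediction.** If the place of recording goes with severity or stroke type, vigilance may go with it too.
- **Localisation.** Widespread sleep slowing could add apparent slow regions or reduce the contrast of a true one.

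**Working it through.** **1. Text check.** The plan states no figure for slowing, sleep or vigilance, so there is nothing of its own to reproduce. Set side by side, the passages give this chain:

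| Step | What the plan specifies | Vigilance handled? |
|---|---|---|
| Instruction (section 3) | Rest means trying to sleep | No; sleep is invited |
| Resting block (section 3) | 10 minutes, no state condition | No |
| Screening (section 4) | Eye, head and muscle artifact | No |
| Slowing analysis (section 4) | Slow regions taken as stroke regions; recording not named | No |
| Band measures (section 4) | Delta and theta shares, ratios, asymmetry | Asymmetry partly; shares and ratios no |

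**2. How a bias would arise.** For a global band share, the spurious difference between two groups or two visits is

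bias = (difference in fraction of epochs asleep) × (sleep-minus-wake change in the share).

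Dividing by the between-person SD gives the bias in SD units. All three inputs below are assumptions.

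- Difference in sleep fraction 20 percentage points, change in delta share 10 points, SD 10 points: 0.20 × 10 = 2 points, and 2 / 10 = 0.2 SD.
- For 0.5 SD with the same SD and the same difference in sleep fraction, the change in delta share must be 0.5 × 10 / 0.20 = 25 points.
- Difference in sleep fraction zero: bias zero, whatever the other inputs.

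**3. What such a bias would do to a test.** Section 10b plans 25 ischaemic and 25 haemorrhagic patients. For a two-sided 5% two-sample t-test with n = 25 per group, there are 48 degrees of freedom, the critical value is 2.011, and the noncentrality is bias × √(n/2) = bias × √12.5 = bias × 3.536.

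| Bias (SD) | Noncentrality | Probability of rejecting with no true difference |
|---|---|---|
| 0 | 0 | 5% |
| 0.2 | 0.707 | 10.7% |
| 0.3 | 1.061 | 18.0% |
| 0.5 | 1.768 | 41.0% |

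I re-ran these figures from the noncentral t distribution. They show how sensitive a comparison of this size would be; they do not predict this trial's error rate. The plan assigns ROC analysis, not a t-test on delta share, to stroke type.

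**The case against.** The case on the other side is substantial.

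- **Slowing is not the sole stroke marker.** It is one of three stroke-specific hdEEG analyses, beside SSEP and EEG-No Source Imaging, and EIT and EIS are separate modalities. This stands.
- **The slowing question is regional.** Sleep slowing is broadly diffuse, so a rule based on regional contrast or asymmetry may be little affected. If such a rule flags a sleeping participant no more often than an awake one, there is no harm to that rule. This stands in part: global shares, percent ratios and global connectivity are also measured and have no such protection.
- **Sleep is not certain.** The resting block lasts 10 minutes, and an instruction to try to sleep does not show that anyone slept. The plan also does not say whether the resting block or the roughly 20 minutes during the sensorimotor assessment feeds the slowing analysis. Both points stand, but drowsiness may be enough, and the second is itself a gap.
- **No hdEEG comparison of stroke patients with controls is specified.** The contrast of all stroke with all healthy participants appears under EIS, and ROC is directed at stroke type. A reader might infer a false-positive rate for 50 patients against 50 controls; the plan names no such hdEEG test, so none is claimed here.
- **The work is exploratory.** Section 10b calls it a pilot, and vigilance could be labelled later from the stored EEG. That lowers the stakes, but labelling afterwards cannot supply awake data that were never recorded.

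**Conclusion.** The point holds as an uncontrolled confounder. The instruction for rest works against one of the stated stroke analyses, and no step in recording, screening or analysis compensates. Drowsiness or sleep may mimic or mask stroke slowing, and may confound comparisons between bedside and laboratory, between stroke types, and between the acute and follow-up visits.

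A reader might go further and infer that sleep activity will be read as pathology, or that the whole stroke assessment depends on it. The documents do not support that: sleep in 10 minutes is not established, the source recording is not named, and slowing is one of several measures, with regional and asymmetry features that help in part.

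The size cannot be determined from the documents. The range of about 11% to 41% at 25 versus 25 depends on an assumed bias of 0.2 to 0.5 SD, which in turn requires that sleep differs between the groups compared. If it does not, the rate stays at 5%.

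**What to change.** For the stroke/control study only:

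1. In section 3, replace the instruction to try to fall asleep with awake, eyes-closed rest for the 10-minute block, and state that it applies to patients and controls and at both visits.
2. In section 4, add a step that labels each epoch awake or drowsy/asleep from the same recording.
3. State that this block feeds the slowing analysis.
4. Compute slowing, band shares and ratios, and asymmetry from awake epochs, and repeat them on all epochs as a sensitivity analysis.

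Leave the corresponding wording for the epilepsy recordings as it is. Recording the state and stratifying by it would be a workable alternative to restriction.

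The cost is one changed instruction and one epoch-selection step, with no new visit or device. Some minutes of the resting block will be discarded, and a few participants may have little awake data; their number should be reported.
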